9.5 Analysis of Secondary Endpoints

Renal allograft rejection rate will be estimated as the proportion of subjects who experience markers of allograft rejection as defined in Section 7.2.

Allograft loss is defined as allograft rejection leading to complete, permanent, and irreversible loss-of-function of the renal allograft. All patients who receive at least one dose of nivolumab will be evaluable for allograft rejection.

Objective response rate (ORR) is defined as the proportion of subjects whose best overall response from baseline is either a CR or PR, based on RECIST 1.1 criteria. ORR will be estimated along with 95% exact CI. A minority of subjects treated with immunotherapy may derive clinical benefit and experience a delayed response, stable disease, or increased OS despite initial evidence of PD with nivolumab or combination treatment. Subjects who continue treatment beyond initial investigator-assessed, RECIST 1.1-defined progression will be considered to have investigator-assessed PD at the time of the initial progression event but may be later designated as delayed responses for purposes of determining ORR and counted as responses. The analysis of ORR will be performed on the response-evaluable population, defined as those subjects who have measurable disease at baseline, receive at least one dose of nivolumab, and undergo response assessments at ~8 and ~16 weeks. Patients who, in the opinion of the investigator, experience PD prior to 16 weeks will also be evaluable. Immune-related ORR based on immune-related response criteria (iRECIST) will also be summarized using the same method.

Among the patients who experience CR or PR, DOR is measured from the time criteria are met for CR/PR (whichever is first recorded) until the first date that recurrent disease or PD is documented. DOR will be summarized using the Kaplan-Meier method. All patients who experience CR/PR will be evaluable for DOR.

Overall survival (OS) is the time from the first dose of nivolumab to the date of death from any cause. A subject who has not died will be censored at last known date alive. Progression-free survival (PFS) is defined as the time from the first dose of nivolumab to the date of the first documented tumor progression or death due to any cause, whichever occurs first. Subjects who did not progress or die will be censored on the date of their last evaluable tumor assessment. Kaplan-Meier curves will be used to summarize OS and PFS. OS and PFS analyses will be performed for all patients who receive at least one dose of nivolumab.

Because the number of patients who change over to nivolumab + ipilimumab or continue nivolumab with reduction in their immunosuppressive regimen after disease progression on nivolumab monotherapy will be small and unpredictable, data from these patients will be considered investigative and potentially hypothesis-generating.

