7.1 Nivolumab and Ipilimumab Dose Modifications

Below are dose modification tables for nivolumab and combination nivolumab with ipilimumab for the following adverse events. Please use as written and contact the drug monitor for any proposed changes.

Please refer to Appendix B, the Nivolumab Investigator's Brochure, or the Ipilimumab Investigator's Brochure for toxicity management algorithms which include specific treatment guidelines. These algorithms should be followed unless there are specific clinical circumstances for which the treating physician decides an alternative treatment approach is clinically appropriate. Consultation with the study PI or drug monitor is recommended.

In several places there are differences from the algorithms regarding protocol directed drug modifications and these are identified with (#). In these cases, please follow the protocol-specific guidelines in this section.

Generally, early evaluation while withholding drug, and appropriate treatment as indicated in the management tables and event specific guidelines is strongly encouraged.

- Any patient with grade 2 drug-related uveitis, eye pain, or blurred vision that does not respond to topical therapy and does not improve to grade 1 severity within the re-treatment period OR that requires systemic treatment should go off protocol therapy
- Patients with any AE, laboratory abnormality, or intercurrent illness which, in the judgment of the investigator, presents a substantial clinical risk to the patient with continued study drug dosing should go off protocol therapy.
- Any grade 3 or 4 drug-related laboratory abnormality or electrolyte abnormality that can be managed independently from underlying organ pathology with electrolyte replacement, hormone replacement, or insulin therapy, or that does not require treatment **does not** require discontinuation of protocol therapy.
- If any kidney-related AEs (e.g. elevated serum creatine levels, development of DSA or non-HLA antibodies, or development of severe proteinuria [>1 g/day]) are observed, nivolumab should be held, a renal allograft biopsy should be obtained, and treatment for allograft rejection should be started immediately (see Section 7.2).

Skin Rash and Oral Lesions	Management/Next Dose for Nivolumab and Combination Nivolumab/Ipilimumab
≤ Grade 1	No change in dose*
Grade 2	Hold* until ≤ grade 1 (#). Resume at same dose level.
Grade 3	Hold* until ≤ grade 1. Resume at same level at investigator's discretion

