7.2 Prednisone and Tacrolimus Dose Modifications for Allograft Rejection

Given the potential for rejection due to the administration of nivolumab and ipilimumab in this study, patients should be monitored closely for signs of rejection.

Markers of allograft rejection may include the following:

- Unexplained $\geq 20\%$ increase in serum creatinine over baseline,
- Development of donor-specific antigen (DSA) or non-HLA antibodies,
- Development of severe proteinuria (>1 g/day),
- Persistent increase in dd-cfDNA.

Serum creatinine (included in the comprehensive metabolic panel) will be monitored according to the schedule outlined in the treatment calendars (Section 11).

Donor-specific and non-HLA antibodies should be checked as clinically indicated at the direction of the institution's transplant nephrologist. Patients should be encouraged to report possible symptoms of rejection, including elevated temperature, elevated blood pressure, graft tenderness, and blood in the urine. Although experimental in this setting, dd-cfDNA levels (see Section 2.5.3 and the Biomarker Plan, Section 5.6) may be useful to monitor for signs of rejection.

Dipstick urinalysis should be performed per the schedule outlined in the treatment calendars. If 2+ or greater, a urine protein/creatinine ratio (spot or 24-hour) should be assessed at the direction of the institution's transplant nephrologist.

If rejection is suspected based on the above analyses, the following interventions will be triggered:

1. Hold or discontinue nivolumab (and ipilimumab, if applicable)
2. Immediately biopsy the renal allograft
 - a. If cell-mediated rejection: Increase the tacrolimus dose (target trough level = 5-10 ng/mL) and administer 500 mg IV methylprednisolone daily for 3 days, with a prednisone taper thereafter. If no improvement, administer 5 mg/kg infliximab.
 - b. If antibody-mediated rejection: Increase the tacrolimus dose (target trough level = 5-10 ng/mL), perform plasmapheresis, and administer IV immunoglobulin (Ig) per institutional protocol plus 500 mg IV methylprednisolone daily for 3 days with a prednisone taper thereafter.

A patient who experiences clinical benefit from the above regimen and still has a functional kidney allograft may restart study therapy after re-screening and consultation with the PI if the patient:

- Experienced an objective response or SD on study therapy,
- Experiences progressive or recurrent disease after having been off study therapy, and

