9.6.3 Evaluation of Allograft

Allograft rejection will be reported as 1) rejection without loss; 2) rejection with loss; or 3) no rejection.

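### The allograft rejection rate in Section 9.5 counts Section 7.2 markers and takes no account of the biopsy, so it measures suspected rejection under the label of rejection

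*Combined protocol and SAP*

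**What the plan says.** Section 9.1.3 lists the allograft rejection rate among the secondary endpoints. Section 9.5 gives the numerator: "Renal allograft rejection rate will be estimated as the proportion of subjects who experience markers of allograft rejection as defined in Section 7.2". It also gives the denominator: "All patients who receive at least one dose of nivolumab will be evaluable for allograft rejection".

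Section 7.2 opens its list with "Markers of allograft rejection may include the following" and names four items: an unexplained creatinine rise of at least 20%, new donor-specific or non-HLA antibodies, proteinuria above 1 g/day, and a sustained rise in dd-cfDNA, which the same section calls experimental in this setting. It continues: "If rejection is suspected based on the above analyses, the following interventions will be triggered". The second intervention is an immediate biopsy of the graft, followed by branches for cell-mediated and antibody-mediated rejection. There is no branch for a biopsy that shows neither. For kidney-related adverse events, Section 7.1 says that "nivolumab should be held, a renal allograft biopsy should be obtained, and treatment for allograft rejection should be started immediately". Section 5.4.3 lets a patient decline the kidney biopsy and remain on study.

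Section 9.6.3 sets the reporting classes: "Allograft rejection will be reported as 1) rejection without loss; 2) rejection with loss; or 3) no rejection". It does not say whether rejection there means markers, histology or clinical judgement.

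**The concern.** In Section 7.2 the markers are grounds for suspicion, and the biopsy is the next step. Section 9.5 stops at the markers and calls the result the rejection rate. A patient whose creatinine rises, who is biopsied at once and whose biopsy shows no rejection stays in the numerator.

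Such patients are plausible on the protocol's own lists. Section 10.1.1 lists raised creatinine as a possible effect of nivolumab, and Section 2.4 says that trials of these drugs excluded transplant recipients, so those rises were presumably not graft rejection. Section 10.1.4 lists abnormal renal function among the commonest reactions to tacrolimus, which is part of the study regimen. Section 2.5.3 says that the utility of dd-cfDNA in this population is unknown, yet a sustained rise is one of the four markers.

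At stake is the meaning of a safety figure that readers will want, because Section 2.4 describes the existing data in transplant recipients as scarce.

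**Working it through.** **Is the primary design touched?** Section 9.1.1 enrols 9 patients, continues with 2 or more successes, adds 7, and rejects the null hypothesis with 5 or more of 16. The probability of rejecting at success rate p is

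sum over x = 2 to 9 of P(Bin(9, p) = x) × P(Bin(7, p) ≥ max(0, 5 − x)).

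At p = 0.15 this is 0.0743 (plan: 0.074). At p = 0.40 it is 0.815 (plan: 0.8). Both stated figures reproduce. The success definition uses allograft loss, not rejection, so neither depends on how rejection is counted.

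**How each type of patient is counted** (dosed with nivolumab, no allograft loss):

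| Patient | Section 9.5 as written | 9.6.3 read with the 9.5 rule | 9.6.3 read histologically |
|---|---|---|---|
| Marker, biopsy shows rejection | rejection | rejection without loss | rejection without loss |
| Marker, biopsy shows no rejection | rejection | rejection without loss | no rejection |
| Marker, biopsy declined | rejection | rejection without loss | no clear class |
| No marker, no biopsy | not counted | no rejection | no rejection |

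The second row is the defect, and it is present in Section 9.5 whichever way Section 9.6.3 is read. If 9.6.3 follows the marker rule, it repeats the misclassification. If it is read histologically, it can differ from 9.5 and has no clear place for the third row.

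**Size per patient.** The denominator is 16, or 9 if the trial ends after stage 1, assuming every enrolled patient receives a dose. One patient is 1/16 = 6.25 points or 1/9 = 11.1 points.

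**Illustrations with assumed counts.** Section 9.5 gives no confidence interval for the rejection rate. The exact (Clopper-Pearson) 95% limits below are added here: lower = Beta quantile 0.025 with (x, n − x + 1), upper = Beta quantile 0.975 with (x + 1, n − x).

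| Assumed patients | n | Marker count | Biopsy-based count |
|---|---|---|---|
| One marker-positive, biopsy-negative; no other suspected case | 16 | 1/16 = 6.25% (0.16 to 30.23%) | 0/16 = 0% (0 to 20.59%) |
| Same | 9 | 1/9 = 11.11% (0.28 to 48.25%) | 0/9 = 0% (0 to 33.63%) |
| The same patient plus one biopsy-proven case | 16 | 2/16 = 12.50% (1.55 to 38.35%) | 1/16 = 6.25% (0.16 to 30.23%) |
| Same | 9 | 2/9 = 22.22% (2.81 to 60.01%) | 1/9 = 11.11% (0.28 to 48.25%) |

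**How many such patients?** The documents do not say. Section 10.1.1 puts raised creatinine in its column of at most 20%, a ceiling of 0.20 × 16 = 3.2 patients (0.20 × 9 = 1.8). That is not an estimate, and the column is not tied to the 20% rise in Section 7.2. Immune-mediated nephritis is listed at under 3%, so under 0.03 × 16 = 0.48 patients.

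**The case against.** The strongest reply is that the marker rule is deliberate and workable. It covers every dosed patient and does not depend on consent to biopsy. Section 7.1 calls for rejection treatment at once for kidney-related events, so the marker count roughly describes who is managed as having rejection. Section 2.5.3 also points to Section 7.2 for the clinical measure of rejection. Histology has its own place as an exploratory objective and as the first-priority biomarker in Section 5.6. All of this is a good reason to keep the marker rate. It does not justify calling it the rejection rate when a biopsy result is in hand. Section 2.5.3 in fact adds to the difficulty: dd-cfDNA is to be judged against Section 7.2 metrics that include dd-cfDNA.

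A reader might go further and infer that Sections 9.5 and 9.6.3 contradict each other, so that the trial will publish two rejection counts. The documents do not support that. Section 9.6.3 never mentions biopsy. Read with the marker rule, it agrees with 9.5 and gives a patient who declines biopsy a class. Two counts arise only on the histological reading.

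A reader might also infer that false positives will be common. No frequency is given, and three of the four items carry limiting words: the creatinine rise must be unexplained, the proteinuria severe and the dd-cfDNA rise persistent. These will remove some cases. They do not let a negative biopsy remove a patient already counted.

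Finally, since "Allograft loss is defined as allograft rejection leading to complete, permanent, and irreversible loss-of-function of the renal allograft", a reader might infer that the primary endpoint is affected. The point concerns the count of rejections, no biopsy is required for loss, and the change below leaves the loss definition alone.

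**Conclusion.** The point holds in this form: the Section 9.5 rule can report a biopsy-negative patient as a rejection, and the endpoint is therefore a rate of suspected rejection. Section 9.6.3 is ambiguous because it does not define the term.

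The size is 6.25 points per affected patient with 16 patients and 11.1 points with 9. The number affected is unknown. The conclusion rests on the supplied text containing no rule that brings the biopsy result into the count; the case report form is not shown.

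The importance is minor to moderate. The endpoint is descriptive, Section 1.2 names allograft loss and not rejection as the objective, and the primary endpoint, type 1 error and power do not change.

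**What to change.** In Section 9.5, among all patients who receive at least one dose of nivolumab, report with exact 95% confidence intervals:

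- (a) *Confirmed rejection*: rejection on allograft biopsy, or allograft loss as Section 9.5 defines it. Give this twice on the same denominator, with suspected patients who had no biopsy or a non-diagnostic one (and no loss) counted first as non-rejections and then as rejections.
- (b) *Suspected rejection*: at least one of the four markers named in Section 7.2, treated as a closed list for this analysis. This keeps the present rate under its correct label.

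In Section 9.6.3, use the same definition with four classes:

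1. confirmed rejection without loss;
2. rejection with loss;
3. no rejection, with suspected but biopsy-negative patients on a sub-line;
4. suspected, no biopsy or a non-diagnostic one, no loss.

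Classes 1 + 2 then equal the lower version of (a), and classes 1 + 2 + 4 the upper version. Leave the clinical triggers and management in Sections 7.1 and 7.2 unchanged.

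The cost is a little more tabulation and a check that the case report form records whether a biopsy was done or refused and what it showed. The biopsies are already planned. Patients who decline biopsy remain undetermined, which is why (a) is given both ways. Rate (b) has its own weakness, because "Donor-specific and non-HLA antibodies should be checked as clinically indicated at the direction of the institution's transplant nephrologist", so it partly reflects how often each site tests. Neither rate is enough alone.

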3. PATIENT SELECTION

3.1 Eligibility Criteria

3.1.1 Patients must be kidney transplant recipients with a functioning allograft who do not currently require dialysis.

3.1.2 Patients must have histologically or cytologically confirmed melanoma, basal cell carcinoma, Merkel cell carcinoma, cutaneous squamous cell carcinoma, or MSI-high cancers for which standard non-immunological medical, surgical, or radiation therapy would be insufficient (*i.e.*, patients who are not surgical candidates). This trial is not intended to provide therapy as a neoadjuvant approach.

3.1.3 Measurable disease as defined by RECIST 1.1 criteria, *i.e.*, at least one lesion that can be accurately measured in at least one dimension (longest diameter to be recorded for non-nodal lesions and short axis for nodal lesions) as ≥ 20 mm by chest x-ray or as ≥ 10 mm with CT scan, magnetic resonance imaging (MRI), or calipers by clinical exam is preferred, but not required. Patients with evaluable disease but no target lesions (*e.g.*, evaluable bone metastases) may be included after discussion with the Principal Investigator (PI). See Section 12 for detailed criteria.

3.1.4 Patients must have documentation, in consultation with the PI, that they received, refused, or were ineligible for the following non-immunologic therapies:

For patients with:	Prior therapies include:
BRAF-mutant melanoma	BRAF/MEK inhibitors
Merkel cell carcinoma	Platinum + VP-16
Basal cell carcinoma	Hedgehog pathway inhibitors
Cutaneous squamous cell carcinoma	Cetuximab
MSI colorectal carcinoma	FOLFOX

3.1.5 Patient's age must be ≥ 18 years. Because no dosing or AE data are currently available on the use of nivolumab and ipilimumab in kidney transplant recipients <18 years of age, children are excluded from this study, but may be eligible for future pediatric trials.

3.1.6 Patients must have ECOG performance status ≤ 2 (Karnofsky $\geq 60\%$), see Appendix A, Performance Status Criteria.

3.1.7 Patients must have normal organ and marrow function as defined below:

- leukocytes	$\geq 2,000/\text{mcL}$
- absolute neutrophil count	$\geq 1,500/\text{mcL}$
- platelets	$\geq 100,000/\text{mcL}$

- total bilirubin $\leq 1.5 \times$ institutional upper limit of normal (ULN)
- AST(SGOT)/ALT(SGPT) $\leq 2.5 \times$ institutional ULN
- serum creatinine $\leq 3 \times$ ULN

Note: patients with creatinine levels above $3 \times$ ULN may be eligible after consultation with the study PI.

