9. STATISTICAL CONSIDERATIONS

9.1 Study Design/Endpoints

9.1.1 Overview

A “success” rate (CR/PR/SD without allograft loss at 16 weeks) of 15% or lower (null hypothesis) would be considered insufficient for further study in this population, while a “success” rate of 40% or higher (alternative hypothesis) would be considered worthy of further investigation. This trial will be performed using a modified Simon’s two-stage minimax design (Simon, 1989). In the first stage, nine patients will be enrolled. To minimize risk to patients, accrual will be paused after the ninth patient is enrolled until a decision is made to continue the trial. If one or no patients experience CR/PR/SD without allograft loss at 16 weeks, the study will be temporarily closed to accrual for futility. Otherwise, 7 additional patients will be enrolled for a total of 16. The null hypothesis will be rejected if 5 or more patients experience CR/PR/SD without allograft loss. This design yields a type 1 error rate of 0.074 and power of 0.8 to distinguish between the null hypothesis and the alternative hypothesis.

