9.1.2 Primary Endpoint

The percentage of kidney transplant recipients with selected advanced cancers for whom standard medical, surgical or radiation therapy would be insufficient who experience CR/PR/SD without allograft loss at 16 weeks after administration of nivolumab, tacrolimus, and prednisone.

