9.4 Analysis of Primary Endpoints

The percent of kidney transplant recipients who experience CR/PR/SD at 16 weeks and do not experience allograft loss after administration of nivolumab, tacrolimus, and prednisone will be calculated, along with the corresponding exact 95% CI. A minority of subjects treated with immunotherapy may derive clinical benefit and experience a delayed response, stable disease, or increased OS despite initial evidence of PD with nivolumab or combination treatment. Subjects who continue treatment beyond initial investigator-assessed, RECIST 1.1-defined progression will be considered to have investigator-assessed PD at the time of the initial progression event but may be later designated as delayed responses for purposes of determining CR/PR/SD and counted as responses for this study.

The evaluable population for the primary endpoint is all subjects who receive at least one dose of nivolumab and undergo tumor response assessments and graft assessments at ~8 and ~16 weeks. Patients who experience allograft loss within 16 weeks of receiving nivolumab will be evaluable for the primary endpoint even if tumor response assessments cannot be performed. Patients who, in the opinion of the investigator, experience PD (with or without allograft failure) prior to 16 weeks will also be evaluable.

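### Allograft loss is defined only as loss caused by rejection, so a graft permanently lost to another cause can be scored as a primary success

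*Combined protocol and SAP*

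**What the plan says.** Section 9.1.2 defines the primary endpoint as the percentage of patients "who experience CR/PR/SD without allograft loss at 16 weeks" after nivolumab, tacrolimus and prednisone. Section 9.4 analyses "The percent of kidney transplant recipients who experience CR/PR/SD at 16 weeks and do not experience allograft loss after administration" of the regimen.

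Both decision rules in Section 9.1.1 count the same event. At stage 1 (nine patients): "If one or no patients experience CR/PR/SD without allograft loss at 16 weeks, the study will be temporarily closed to accrual for futility". At the end (16 patients): "The null hypothesis will be rejected if 5 or more patients experience CR/PR/SD without allograft loss".

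Section 9.4 also has an evaluability exception, for cases where tumour assessment is not possible: "Patients who experience allograft loss within 16 weeks of receiving nivolumab will be evaluable for the primary endpoint even if tumor response assessments cannot" (sentence cut here).

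Neither 9.1 nor 9.4 says what allograft loss is. The definition comes in Section 9.5, under the secondary endpoints: "Allograft loss is defined as allograft rejection leading to complete, permanent, and irreversible loss-of-function of the renal allograft". I found no other. Section 9.4 also speaks of allograft failure, which is not defined.

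Section 9.6.3 gives three reporting categories: rejection without loss, rejection with loss, and no rejection.

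**The concern.** Entry to the trial is judged on function: "Patients must be kidney transplant recipients with a functioning allograft who do not currently require dialysis". Loss is judged on cause. A patient who enters with a working graft and ends permanently without one has not lost the allograft, in the plan's terms, unless rejection was responsible.

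Two things follow on a literal reading.

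- A patient with CR/PR/SD at week 16 and a graft permanently lost to another attributed cause is a primary success, and Section 9.6.3 would report that patient as having no rejection.
- If such a loss prevents the tumour assessments, the Section 9.4 exception does not apply. Absent progression, the patient leaves the denominator and is not counted as a failure.

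The plan's own risk lists show that the case can arise. Section 10.1.1 lists acute kidney injury and immune-mediated nephritis for nivolumab, and Section 10.1.4 lists abnormal renal function for tacrolimus. The endpoint is meant to count tumour control with a working graft, so scoring these patients as successes works against its purpose.

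**Working it through.** **1. Which rule decides a loss?**

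| Place | What it does | What it leaves open |
|---|---|---|
| 9.5, rejection rate | Counts patients with the Section 7.2 markers | Written for the rate, not for the cause of a loss |
| 9.5, loss | Requires rejection as the cause | Does not say how cause is established |
| 7.2, markers | Creatinine rise, antibodies, proteinuria, dd-cfDNA | The list is open-ended; the creatinine marker covers only rises without an explanation |
| 7.1, kidney events | "nivolumab should be held, a renal allograft biopsy should be obtained, and treatment for allograft rejection should be started immediately" | A biopsy can point to a cause other than rejection |
| 5.4.3, biopsy | Allows refusal | Cause may then stay unknown |

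Nothing ranks the markers against the attributed cause, so two careful readers can classify the same patient differently.

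**2. Reproduce the stated design.** Inputs from Section 9.1.1: n1 = 9, stop if 1 or fewer successes; n = 16, reject the null if 5 or more; p0 = 0.15, p1 = 0.40.

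P(reject) = sum over x = 2 to 9 of P(X1 = x; 9, p) × P(X2 ≥ max(0, 5 − x); 7, p)

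- At p = 0.15: 0.0743 (stated 0.074).
- At p = 0.40: 0.815 (stated 0.8).
- P(stop at stage 1) at p = 0.15: 0.85^9 + 9 × 0.15 × 0.85^8 = 0.2316 + 0.3679 = 0.5995.

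The plan's figures reproduce.

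**3. Size of the effect.** The documents give no rate of permanent non-rejection graft loss. Section 10.1.1 places immune-mediated nephritis in the below-3% column. That figure covers any outcome, is not specific to transplant recipients, and is for one term only. I therefore use assumed values up to 3%.

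Let q be the share of scored successes who in fact have such a loss. With a true any-cause success rate of 0.15:

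- scored rate p = 0.15 / (1 − q)
- share of all patients affected m = p − 0.15
- P(at least one in 16) = 1 − (1 − m)^16

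| q (assumed) | Scored rate p | P(declare success) | P(stage 1 stop) | P(at least one in 16) |
|---|---|---|---|---|
| 0 | 0.1500 | 0.0743 | 0.5995 | 0 |
| 0.5% | 0.1508 | 0.0756 | 0.5969 | 0.012 |
| 1% | 0.1515 | 0.0770 | 0.5942 | 0.024 |
| 3% | 0.1546 | 0.0827 | 0.5835 | 0.072 |

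A harsher assumption applies the rate to all patients, all of them scored as successes. At 1% the scored rate is 0.16 and P(declare success) is 0.093; at 2% it is 0.17 and 0.114. That 1% equals 0.01/0.16 = 6.25% of scored successes, well above the range in the table.

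**4. How close the boundaries are.** One reclassified patient turns 1/9 (stop) into 2/9 (continue), or 4/16 (do not reject) into 5/16 (reject). At a true 15%:

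- P(exactly 1 of 9) = 9 × 0.15 × 0.85^8 = 0.368
- P(pass stage 1 and end at exactly 4 of 16) = 0.106

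These are the chances of sitting one patient from a boundary, not of a changed decision. A changed decision also needs such a patient to occur.

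**The case against.** The strongest reply is that the plan largely handles this in practice. The sentence just before the definition counts rejection by the Section 7.2 markers, and those markers are broad. Section 7.1 starts rejection treatment for kidney-related events and refers every renal grade to Section 7.2, where the biopsy branches are only cell-mediated and antibody-mediated rejection. Section 5.6 treats dd-cfDNA as an indicator of kidney injury in general. Most permanent losses would therefore be labelled rejection with loss and count as failures. Sections 6.2 and 6.3 also mention allograft loss with no cause attached, and Section 7.2 links it to dialysis. That suggests the authors meant loss of function and drafted loosely. A rejection-specific component could also be deliberate, since rejection is the stated worry in the background and rationale.

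Much of this stands. It narrows the reach and makes an intention to score lost grafts as successes unlikely. It does not close the gap. The marker sentence governs the rejection rate and not the cause of a loss, the marker list is not exhaustive, and an explained creatinine rise falls outside its marker. If any-cause loss was intended, the definition says something else. If a rejection-specific component was intended, immune-mediated nephritis is still a listed risk of the study drug, and a patient who loses the graft to it is hard to call a success.

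**Conclusion.** The concern holds. The only definition of a term that carries the primary endpoint, both decision rules and an evaluability exception makes rejection a condition of loss. On its words, a permanent non-rejection loss in a patient with CR/PR/SD is a success.

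The expected bias is small: under the assumed 0.5% to 3% of scored successes, type I error moves from 0.074 to 0.076–0.083 and the futility-stop probability from 0.599 to 0.597–0.583. Those shares are assumptions. The one rate in the documents covers one listed term in a general population, so it bounds neither the transplant rate nor other causes. What makes the point worth acting on is that, with 9 and then 16 patients, one disputed classification can settle the trial's conclusion. It should be corrected, but it does not threaten the design.

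**What to change.** - In Sections 9.1.2 and 9.4, define allograft loss for the primary endpoint as complete, permanent loss of graft function from any cause.
- State that the Section 9.1.1 futility and rejection counts and the Section 9.4 evaluability exception use this definition, so that such a patient is evaluable and counts as a failure.
- Use one defined term in place of both allograft loss and allograft failure.
- Keep rejection-caused loss as a secondary sub-category, add a category for loss without rejection to Section 9.6.3, and state whether the Section 7.2 markers or the attributed cause decides between them.

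The cost is wording only. The sample size (9, then 16) and the boundaries (more than 1 of 9, at least 5 of 16) stay as they are. The stated 0.074 and 0.8 also stand, because the 15% and 40% rates then refer to the any-cause endpoint. No treatment rule is touched. The downside is that losses unrelated to rejection, including some unrelated to treatment, will count as failures and may lower the observed success rate slightly; the sub-category keeps the rejection-specific result visible.
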